### 11.2. Exclusion Criteria

1. Females who are pregnant or breast-feeding
2. Patients with an impending, life-threatening cerebral herniation syndrome, based on the assessment of the study neurosurgeons or their designate
3. Patients with severe, active co-morbidity, defined as follow:

- a) Patients with an active infection requiring intravenous treatment or having an unexplained febrile illness (Tmax > 99.5°F/37.5°C)
- b) Patients with known immunosuppressive disease or known uncontrolled human immunodeficiency virus infection
- c) Patients with unstable or severe intercurrent medical conditions such as severe heart disease (New York Heart Association Class 3 or 4)
- 4. Patients who have not recovered from the toxic effects of prior chemo- and/or radiation therapy.
- 5. Patients must not have received immunotherapy within 3 months prior to enrollment
- 6. Patients with prior, unrelated malignancy requiring current active treatment in the last 3 years with the exception of cervical carcinoma *in situ* and adequately treated basal cell or squamous cell carcinoma of the skin
- 7. Patients with a known history of hypersensitivity to nivolumab, or any components of nivolumab
- 8. Patients with a known history of hypersensitivity to ipilimumab, or any components of ipilimumab
- 9. Patients with active autoimmune disease requiring systemic immunomodulatory treatment within the past 3 months.
- 10. History and/or confirmed pneumonitis, or extensive bilateral lung disease on high resolution/spiral CT scan.

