## 6. STUDY SCHEMA

Arm	Study Drug	Study Drug Administration Schedule	Dose
1	Nivolumab	7 days (±3 days) prior to surgery	3 mg/kg
1	Ipilimumab	7 days (±3 days) prior to surgery	1 mg/kg

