### **9.1.2. Dose Modification**

#### **9.1.2.1. Non-hematologic:**

Not applicable, only one dose of the study drug is given so there will be no intra-patient dose reduction. Similarly, the proposed doses of 3 mg/kg for nivolumab and 1 mg/kg for ipilimumab are recommended by the FDA.

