### **12.6. Early Withdrawal of Subject(s)**

### **12.6.1. Criteria for Early Withdrawal**

Subjects may voluntarily withdraw from the study at any time. The PI may also withdraw a subject from the study at any time based on his/her discretion. Reasons for PI-initiated withdrawal may include, but is not limited to the following:

- If, in the investigator's medical judgment, further participation would be injurious to the subject's health or wellbeing
- Protocol deviation
- Administrative issues
- Non-compliance of the subject
- Pregnancy
- They do not receive neoadjuvant nivolumab and ipilimumab infusions

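### Prior immunotherapy is limited only by a 3-month washout; no entry criterion bars a patient whose checkpoint inhibitor was permanently stopped for a severe immune event other than pneumonitis

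*Combined protocol and SAP*

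**What the plan says.** Only one criterion in Section 11 names prior immunotherapy. It is exclusion 5, and it sets a washout: "Patients must not have received immunotherapy within 3 months prior to enrollment".

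The neighbouring exclusions in Section 11.2 bear on the point as follows:
- Exclusion 3c: "Patients with unstable or severe intercurrent medical conditions such as severe heart disease".
- Exclusion 4: "Patients who have not recovered from the toxic effects of prior chemo- and/or radiation therapy".
- Exclusions 7 and 8: known hypersensitivity to nivolumab or ipilimumab.
- Exclusion 9: "Patients with active autoimmune disease requiring systemic immunomodulatory treatment within the past 3 months".
- Exclusion 10: "History and/or confirmed pneumonitis, or extensive bilateral lung disease on high resolution/spiral CT scan".

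Section 11.1 sets screening limits for clotting times, neutrophils, hemoglobin, platelets and creatinine (inclusions 6-10). It sets none for AST, ALT or bilirubin.

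Section 6 schedules both drugs "7 days (±3 days) prior to surgery". Section 9.1.2 says that "only one dose of the study drug is given so there will be no intra-patient dose reduction". Section 12.6.1 lets the investigator withdraw a patient if "further participation would be injurious" to health. Section 18 gives management tables for immune toxicity, several of which end treatment after severe events.

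**The concern.** The washout implies that previously treated patients are expected, and Section 9.1 restricts histology to tumors known to respond to immunotherapy. Some candidates may therefore have had a checkpoint inhibitor before, and some of those may have stopped it because of toxicity. Section 9.1.3 reports severe immune-related events in about 25-37% of ipilimumab-treated patients in earlier advanced-melanoma studies. That is not a discontinuation rate and not this population, but it shows that such events are not rare.

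The criteria ask how long ago immunotherapy was given. They do not ask why it stopped or, in general, whether its toxicity has resolved. Because each patient gets one dose, the steps in Section 18 that delay or discontinue treatment have no later study dose to act on. Entry is the point at which a mandatory rule could prevent re-exposure. At stake is giving the combination, shortly before brain surgery, to a patient whose earlier event would have ended treatment under the protocol's own tables.

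**Working it through.** There is no figure in the plan to reproduce. The check compares the entry criteria with Section 18.

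**Interval from infusion to surgery (Section 6).** 7 - 3 = 4 days; 7 + 3 = 10 days.

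**Are previously treated patients admitted?** Yes. In inclusion 1, the requirement of no earlier treatment describes the brain metastasis, not the patient's systemic therapy. Exclusion 5 would be needless otherwise.

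**Patient A: resolved severe event.** The checkpoint inhibitor was permanently stopped for Grade 3-4 myocarditis or colitis. The patient has recovered, and the last immunotherapy and last systemic immunomodulatory treatment were each more than 3 months before enrollment.

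| Criterion | Met? | Reason |
|---|---|---|
| Exclusion 3c | No | Condition no longer unstable or severe |
| Exclusion 4 | No | Names chemotherapy and radiation only |
| Exclusion 5 | No | More than 3 months |
| Exclusions 7, 8 | No | Not hypersensitivity |
| Exclusion 9 | No | Outside the 3-month look-back, even if an immune event counts as autoimmune disease |
| Exclusion 10 | No | Not pneumonitis |
| Exclusions 1, 2, 6; inclusions 1-12 | No bar | None asks about earlier immune events |

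Result: no written criterion bars Patient A. For the same events on treatment, Table 9 (Grade 3-4 myocarditis) permanently ends immunotherapy and Table 10 (Grade 3-4 diarrhea or colitis) permanently ends ipilimumab.

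**Patient B: unresolved non-severe event.** Grade 2 immune hepatitis is still present, without systemic treatment and with the laboratory values in inclusions 6-10 within limits. The last immunotherapy was more than 3 months ago. Exclusion 4 does not name immunotherapy, exclusion 3c does not apply if the condition is neither unstable nor severe, and no liver limit exists. Result: not barred. Tables 5 and 11 would both hold treatment at that grade.

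**What existing criteria already catch, whatever the cause:**
- Renal toxicity with creatinine above 1.5 x ULN (inclusion 10).
- Persisting hematologic or coagulation toxicity (inclusions 6-9).
- Any history of pneumonitis (exclusion 10).
- Unstable or severe current conditions (exclusion 3c).
- Some events treated systemically within 3 months, depending on how exclusion 9 is read.
- SJS/TEN, possibly, if read as hypersensitivity (exclusions 7 and 8).

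**What is left:** resolved severe events such as Grade 3-4 myocarditis, colitis or neurological toxicity, and non-severe unresolved hepatic, GI, skin or neurological toxicity.

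**Size.** The documents give neither the share of candidates with earlier checkpoint-inhibitor treatment nor a permanent-discontinuation rate, so no count can be computed.

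**The case against.** The strongest reply is that clinical judgment already covers this. The investigator may withdraw a patient at any time, and Section 12.6.3 replaces anyone who withdraws without receiving both drugs, so withholding treatment costs no evaluable patient. Exposure is a single dose. Sections 7.2.1 and 7.2.2 also refer to the Investigator's Brochures, which may advise on re-exposure; that cannot be checked here. This stands as mitigation. It does not close the gap, because withdrawal under Section 12.6.1 is discretionary and is not an eligibility rule.

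Three stronger readings are tempting and are not supported:
- A reader might infer that no criterion reaches unresolved immunotherapy toxicity at all. Inclusions 6-10 and exclusions 3c, 9 and 10 reach part of it.
- A reader might infer that Sections 11 and 18 contradict each other. Section 18 manages events on treatment and sets no entry criteria, so this is an omission.
- A reader might infer that every discontinuation in Section 18 without a resumption step is a lifetime bar. Only some entries say that the stop is permanent (Tables 7, 9 and 10). For Grade 3-4 hepatitis, the Table 11 footnote allows ipilimumab to resume in some cases where Table 5 discontinues. Letting the stricter table govern would be a clinical preference that the documents do not settle.

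A bare requirement of recovery from immunotherapy toxicity would also go too far. Most of the tables continue treatment at Grade 1, and Tables 6 and 12 resume it after endocrinopathy with or without hormone replacement.

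**Conclusion.** The gap is real and should be closed. As written, Section 11 admits a recovered patient whose checkpoint inhibitor was permanently stopped for a severe immune-related event other than pneumonitis, and some patients with non-severe unresolved immune toxicity. The former rests only on the text of the criteria. The latter also assumes that exclusions 3c and 9 are read by their plain terms. The consequence is possible combination re-exposure 4 to 10 days before brain surgery, with only a discretionary safeguard. How many of the 20 patients this could concern is unknown. Endpoints, analyses and sample size are unaffected.

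**What to change.** 1. Add an exclusion: *History of an immune-related adverse event that led to permanent discontinuation of a checkpoint inhibitor, or for which Section 18 specifies permanent discontinuation (e.g. Grade 3-4 myocarditis, Grade 3-4 colitis, SJS/TEN).* Severe neurological or hepatic events are then caught when they actually led to a permanent stop. Recovered Grade 2 myocarditis, for which Table 9 allows retreatment to be considered, stays eligible unless it led to one.
2. Replace exclusion 4 with: *Toxicity of prior chemotherapy, radiation therapy and/or immunotherapy that has not resolved to Grade 1 or baseline, except endocrinopathy controlled on hormone replacement.*

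The cost is one line added and one reworded. Medical history is already obtained (Section 12.7.1) and a CMP is already drawn at screening (Table 1), so no new test is needed, assuming that the panel includes liver tests as usual. An unknown number of previously treated candidates become ineligible. That matters in a 20-patient trial that reported enrollment difficulty, although Section 15.1 attributes the difficulty to randomization, since removed. The Grade 1 threshold would also bar an unresolved Grade 2 rash, at which Tables 7 and 13 initially continue treatment, and it now applies to chemotherapy and radiation toxicity too. The investigators should confirm that they accept both effects.

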## 12. SCREENING AND ON-STUDY TESTS AND PROCEDURES

**Table 1: Schedule of Study Tests and Procedures**

Description	Screening	Treatment Period				
	Up to 14 days prior to surgical resection	Neoadjuvant IO	Surgery		Adjuvant SRS 	Follow-up
Week 		-1	1	3 	4	7, 13 +SOC visits
Day 		-10 to -4	1	15	22 ( $\pm$ 3 weeks)	29 + SOC visits
General Evaluations						
Informed Consent	X					
Physical Exam 	X	X	X	X		X
Neurologic Exam 	X	X	X	X		X
Performance Status 	X	X	X	X		X
Adverse Events					Continuous 	
Laboratory Evaluations						
CBC w/diff	X	X 	X	X		X
CMP	X	X 	X	X		X
Thyroid panel	X					X
PT, aPTT	X					
Pregnancy test 	X	X 				
Whole blood for correlative analysis (3x10 mL yellow top) 	X		X 	X	X 	X 
Archival tissue sample 	X					
Surgical tissue sample			X 			
Disease Evaluations						
MRI of the brain 	X					X 
Treatment						
Ipilimumab		X				
Nivolumab		X				
Surgery 			X			
SRS					X	

Number of fractions for SRS treatment will be assigned at physician's discretion

Weeks and days listed are approximate.

Post-operative visit

Clinical evaluations will include a general physical examination, complete neurologic examination, and KPS rating.

Adverse events will be continuously monitored after the first study-mandated agent is administered to the patient and reviewed monthly by the study PI. AE collection will cease 100-days after surgery, or 100 days after ipilimumab/nivolumab infusion for patients who do not undergo surgery.

Only drawn if more than 7-days (24-hours for pregnancy) post screening draw

For women of childbearing potential

Whole blood should be sent to the Substrate Services Core (SSCRS) for processing and then sent to [name] laboratory

Blood should be drawn prior to surgical resection

Blood should be drawn prior to SRS

Drawn only at the week 7 follow-up visit

A sample of archival tissue from the primary or other extracranial tumor will be requested for correlative analysis, if available.

A sample of tissue from the resected metastases will be requested for correlative analysis, if available.

MRI of the brain should be accompanied by systemic staging scans per standard of care. Though not dictated by the protocol, results of standard of care systemic staging scans should be recorded in the eCRF.

No MRI taken at week 7. Follow-up MRIs will be taken at week 13 ( $\pm$  2 weeks) and continue every 12 weeks ( $\pm$  4 weeks) thereafter.

Surgery is performed per SOC.

## 12.1. Screening Examination

All screening procedures should occur within 14 days prior to the planned surgical resection. An informed consent form must be signed by the patient prior to initiating any screening tests or procedures. Screening test and procedures include a physical exam, neurological exam, performance (KPS) status, a pregnancy test, and blood tests. Blood for immune monitoring will also be collected during screening. An archival tissue sample from the primary tumor will be requested for correlative analysis, if available.

If a subject does not receive nivolumab or ipilimumab, minimal records regarding the subject will be retained in the study database. Participants who screen fail after providing informed consent but before receiving study-related treatment will be withdrawn, and these subjects will be excluded from all analyses.

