#### **9.1.5. Concomitant Medications**

##### **9.1.5.1. Steroids**

Corticosteroids should be used at the lowest dose to control symptoms of edema and mass effect, and discontinued, if possible. Use of corticosteroids should be recorded in the electronic research database (see Section 16.5). Every effort should be made to keep the dose of steroids at or lower than an equivalent of 4 mg daily of dexamethasone.

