## 12.2. Treatment Period

### Day -10 to -4:

- Physical exam, neurological exam, and KPS
- Laboratory testing including:
  - CBC with differential
  - CMP
  - Beta-HCG, if appropriate and > 24 hours post screening Beta-HCG
- Ipilimumab infusion
- Nivolumab infusion

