#### **15.5.2.1. Variable**

To examine T-cell proliferation rates, Ki67 staining will be performed on PD-1+/CD8+ T cells extracted both from the peripheral blood and from resected tissue.

As described in [Table 1](#) of Section [12](#), blood will be drawn longitudinally during treatment to study how a single dose of nivolumab and ipilimumab before surgery affect T-cell proliferation over time.

The primary outcome is the fold-change in Ki67 levels on peripheral-blood T cells between baseline and Day 1.

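### The co-primary Ki67 fold-change has no infusion-day baseline: the only sample before Day 1 is the screening draw, which may precede dosing by 0 to 10 days

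*Combined protocol and SAP*

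**What the plan says.** All references are to the combined protocol and SAP.

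- **Outcome.** Section 15.5.2.1: "The primary outcome is the fold-change in Ki67 levels on peripheral-blood T cells between baseline and Day 1". Section 8 gives the same endpoint as a mean. Neither section says which sample is the baseline.
- **Screening sample.** Section 12.1: "Blood for immune monitoring will also be collected during screening", and also "All screening procedures should occur within 14 days prior to the planned surgical resection". The screening column of Table 1 is headed "Up to 14 days prior to surgical resection".
- **Infusion.** Section 6 places both drugs "7 days (±3 days) prior to surgery", that is, 4 to 10 days before it.
- **Infusion visit.** In Table 1 the row that begins "Whole blood for correlative analysis (3x10 mL yellow top" is marked at screening and at surgery and is blank in the Neoadjuvant IO column. The Day -10 to -4 list in Section 12.2 has examinations, CBC, CMP, "Beta-HCG, if appropriate and > 24 hours post screening Beta-HCG" and the two infusions, with no immune-monitoring blood.
- **Repeat rule.** Footnote 6 of Table 1 has CBC and CMP redrawn at the infusion visit if the screening draw is more than 7 days old. The correlative blood has no such rule.
- **Steroids.** Section 9.1.5.1: "Corticosteroids should be used at the lowest dose to control symptoms of edema and mass effect, and discontinued, if possible". The same section asks that use be recorded and that the dose be kept at or below the equivalent of 4 mg dexamethasone daily. Inclusion criterion 2 applies a 4 mg limit for at least 7 days before enrollment.
- **Analysis.** Section 15.5.2.2 tests the mean fold-change with a one-sample t-test, with a log transformation or a Wilcoxon test as alternatives. Section 15.1 records that the control arm was removed.

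**The concern.** Hypothesis 2 attributes a rise in Ki67 to neoadjuvant immunotherapy, and Section 7.3 uses this change to establish that the treatment is active. With one arm and an unadjusted one-sample test, the fold-change contains everything that happened between the two samples. When baseline is the screening draw, that includes days on which the patient had received no study drug.

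Ki67 could shift in those days for other reasons, for example a steroid adjustment within the 4 mg limit. A shift in one direction across patients would bias the estimate: upward drift could pass for a drug effect, and downward drift could hide one. Drift that differs from patient to patient without a common direction would cost power.

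The sample-size argument in Section 15.8 rests on a published fold-change measured 7 days after the first dose. Here the baseline is tied to the surgery date and not to the dose. The plan already treats older screening blood as out of date for CBC and CMP at the infusion visit, but not for a primary outcome.

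**Working it through.** **1. Timing.** Inputs: screening at most 14 days before planned surgery (Section 12.1, Table 1); infusion 4, 7 or 10 days before surgery (Section 6). Largest untreated gap = 14 − infusion lead time.

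| Infusion, days before surgery | Largest gap from baseline to infusion | Drug-free share of a 14-day interval |
|---|---|---|
| 4 | 14 − 4 = 10 days | 10/14 = 71% |
| 7 (nominal) | 14 − 7 = 7 days | 7/14 = 50% |
| 10 | 14 − 10 = 4 days | 4/14 = 29% |

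The smallest gap is 0, when screening and infusion coincide. The treated interval is 4 to 10 days.

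**2. The plan's own power figure.** Section 15.8 gives n = 17, CV 0.6, fold-change 1.7, two-sided 0.05 and power above 95%.

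- Log scale: SD = √ln(1 + 0.6²) = 0.5545; noncentrality = ln(1.7)/0.5545 × √17 = 3.95; critical t on 16 df = 2.12; power 95.9%. The stated figure reproduces.
- Raw scale against a null of 1, with SD = 0.6 × 1.7 = 1.02: noncentrality = 0.7/1.02 × √17 = 2.83; power 75.7%. The stated figure therefore matches the log scale, not the untransformed test that Section 15.5.2.2 names first. Both scales are shown below for that reason.

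**3. Illustration: no drug effect, systematic untreated rise.** The rises are assumptions; the documents give none. The chance of a significant increase is the upper tail of the noncentral t with noncentrality

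- log scale: ln(f)/0.5545 × √17, with f the geometric mean fold-change;
- raw scale: (f − 1)/(0.6f) × √17, with f the arithmetic mean.

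| Assumed rise f | Noncentrality, log | Significant increase, log | Noncentrality, raw | Significant increase, raw |
|---|---|---|---|---|
| 1.0 | 0 | 2.5% | 0 | 2.5% |
| 1.1 | 0.71 | 9.8% | 0.62 | 8.5% |
| 1.2 | 1.36 | 24.7% | 1.15 | 18.9% |
| 1.3 | 1.95 | 45.0% | 1.59 | 32.0% |

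**4. Illustration: true 1.7-fold drug effect, log scale.**

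- Systematic fall before the infusion: multiplying 1.7 by 0.9, 0.8 or 0.7 gives 1.53, 1.36 or 1.19. Power falls from 95.9% to 84.3%, 57.5% or 22.9%.
- Drift with no common direction: the SD becomes √(0.5545² + ln(1 + c²)). With c = 0.2, 0.3 or 0.5, power is 93.6%, 90.5% or 80.5%.

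**The case against.** The case against giving this much weight is substantial.

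- **Ten days is a corner case.** It needs the earliest screening and the latest infusion together. If both windows were filled uniformly (an assumption), the mean gap would be about 3.5 days, and about 17% of patients would have a gap longer than their treated time. This stands. The gap should be read as 0 to 10 days.
- **The steroid route is partly closed.** The 4 mg limit applies before enrollment and every effort is to be made to keep to it on study, and steroid use is already recorded. The steroid advice is also general, so a reduction could just as well follow the infusion. This limits the size of a steroid effect. It does not exclude one, because the dose is capped and not required to be stable.
- **Prior therapy is partly covered.** Exclusion 4 bars patients not recovered from the toxic effects of chemotherapy or radiation, and exclusion 5 bars immunotherapy within 3 months. Carry-over from earlier treatment is therefore a weaker source of drift than a reader might suppose.
- **The drift sizes are invented and must run one way.** Opposing drifts across 17 patients with mixed histologies would tend to cancel, leaving noise and not bias. The percentages also depend on scale: if the data are log-normal with those arithmetic means, the raw t-test gives about 3%, 11% and 26%. This stands, and the figures show sensitivity only.
- **Baseline may be defined in the Correlative Lab Manual,** which is not in these documents. However, Section 9.3 refers the timing of the blood draws to Table 1, and Table 1 has no infusion-day draw.

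None of these points is a reason to keep the gap when an existing visit can close it.

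**Conclusion.** The schedule gap is certain: Table 1 and Section 12.2 agree that no correlative blood is taken on the infusion day. That screening is the baseline is an inference, though the only one available, since it is the sole sample before Day 1. The consequence is a possible bias or loss of precision in a primary outcome, of unknown size and direction. The change should be made because it is cheap, not because harm has been shown.

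The documents do not support some stronger readings:

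- **That there is no pre-treatment sample.** The screening sample is itself pre-dose; what is missing is a sample on the infusion day.
- **That most of the interval is typically drug-free.** At nominal infusion timing the untreated share is at most half, and it can be zero.
- **That the false-positive rate is 10% to 45%.** Those figures follow only from assumed systematic rises, on the log scale, with n = 17 and CV 0.6.
- **That an infusion-day sample would isolate the drug effect.** The 4 to 10 days from infusion to Day 1 stay uncontrolled because the trial is single-arm.

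**What to change.** 1. Collect the correlative tubes at the infusion visit, before the first drug, either by moving the screening draw or by adding one. Show this in Table 1 and in the Day -10 to -4 list of Section 12.2; amend Section 12.1 if the draw is moved.
2. Define baseline in Section 8, Table 1, Section 12.2 and Section 15.5.2.1 as the last sample before the first infusion. If both samples are kept, the screening sample is the fallback when the infusion-day sample is missing, and the change between the two gives a direct estimate of untreated drift.
3. Record the interval from baseline sample to infusion and the steroid dose at each draw. Steroid use is already captured, so this only adds the dose on the draw date. Report both alongside the fold-change.

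The cost is a protocol amendment and at most one extra set of tubes at a visit the patient already attends; moving the draw needs no extra tubes but leaves no fallback sample. The sample cannot be obtained once a patient has been dosed, so the amendment helps only patients not yet treated. If pre-infusion drift is nil, the log-scale power stays at 95.9%, so nothing is lost.
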